10. TREATMENT OF SUBJECTS

Subjects will be randomized with a randomization ratio of at least 2:1 to receive either ATB200/AT2221 or alglucosidase alfa/placebo according to the treatment assignment in [Table 8](#).

Table 8: Treatment Assignment

Treatment Assignment	Treatment	Regimen
ATB200/AT2221	AT2221 ^a	Subjects \geq 50 kg: 260 mg (4 \times 65-mg oral capsules) 1 hour prior to ATB200 infusion every 2 weeks Subjects \geq 40 kg to < 50 kg: 195 mg (3 \times 65-mg oral capsules) 1 hour prior to ATB200 infusion every 2 weeks
	ATB200	20 mg/kg IV infusion over a 4-hour duration every 2 weeks
Alglucosidase alfa/placebo	Placebo	Subjects \geq 50 kg: Placebo (4 oral capsules) 1 hour prior to alglucosidase alfa infusion every 2 weeks Subjects \geq 40 kg to < 50 kg: Placebo (3 oral capsules) 1 hour prior to alglucosidase alfa infusion every 2 weeks
	Alglucosidase alfa	20 mg/kg IV infusion over a 4-hour duration every 2 weeks

Abbreviations: IV = intravenous

^a Note: Subjects are required to fast at least 2 hours before and 2 hours after administration of AT2221 or placebo.

11. STUDY DRUG MATERIALS AND MANAGEMENT

11.1. Study Drug

Study drug is defined in this protocol as ATB200, AT2221, alglucosidase alfa, placebo, or a combination of these. Investigational product refers only to ATB200, AT2221, or a combination of these.

The study drug will be administered every 2 weeks at the study site in a blinded fashion. After 6 months in the study without any IARs, subjects may be eligible for administration of study drug at their home (see Section 12.2.3). In countries or at sites where the administration of alglucosidase alfa is reserved for hospital use, however, all study drug will be administered in a hospital setting.

ATB200 (rhGAA) functions as ERT. AT2221 (*N*-butyl-deoxynojirimycin) is an iminosugar that functions as a selective small molecule enzyme stabilizer of rhGAA.

Table 9 provides details on the investigational products.

Table 9: Investigational Products

Product name	ATB200	AT2221
Dosage form	Lyophilized powder for IV infusion	Hard gelatin capsule
Unit dose	15 mg/mL	65 mg
Route of administration	IV infusion	Oral
Physical description	Sterile, nonpyrogenic, white to off-white lyophilized cake or powder supplied in single-use, clear 20-mL (cc) glass vials	White, size 2, hard gelatin capsules supplied in 40-cc HDPE bottles
Excipients	sodium citrate dihydrate, citric acid monohydrate, mannitol, polysorbate-80	Microcrystalline cellulose, pregelatinized starch, Emprove [®] sucralose powder, magnesium stearate, colloidal silicon dioxide
Manufacturer	WuXi Biologics Co., Ltd [name]	Alcami [name]

Abbreviations: HDPE = high density polyethylene; IV = intravenous; USA = United States of America

Alglucosidase alfa (Myozyme/Lumizyme) functions as ERT. Its dosage form is lyophilized powder for IV infusion, and its unit dose is 5 mg/mL. It is a sterile, nonpyrogenic, white to off-white lyophilized cake or powder supplied in single-use, clear 20-mL (cc) glass vials. Excipients include mannitol, polysorbate-80, sodium phosphate dibasic heptahydrate, and sodium phosphate monobasic monohydrate. Alglucosidase alfa is manufactured by Genzyme Corporation (Cambridge, MA). Placebo oral capsules match AT2221 in appearance, contain the same excipients as AT2221, and are manufactured by Alcami (Wilmington, NC).

11.2. Study Drug Packaging and Labeling

AT2221 (65 mg capsule) and associated placebo will be supplied by Amicus as hard gelatin capsules in high density polyethylene bottles and will be administered orally.

ATB200 (105 mg/vial) will be supplied by Amicus as a lyophilized powder in glass vials and will be administered by IV infusion upon reconstitution with sterile water for injection and followed by dilution with 0.9% sodium chloride for injection prior to administration. Sterile water for injection and 0.9% sodium chloride for injection will be supplied by the study sites.

Alglucosidase alfa (50 mg/vial) will be supplied by Amicus as a lyophilized powder in glass vials and will be administered by IV infusion upon reconstitution with sterile water for injection and followed by dilution with 0.9% sodium chloride for injection prior to administration. Sterile water for injection and 0.9% sodium chloride for injection will be supplied by the study sites.

Each container will be labeled in conformance to regulatory requirements and, where applicable, local laws. All labels will be printed with the following information at a minimum: study identifier, identity of drug and dosage, sponsor name and contact details (and/or details of a local designee contact), dosing instructions, storage information, and other applicable local law statements. All labels will comply with legal requirements of each country.

11.3. Study Drug Storage

Sites will be instructed to store AT2221 65-mg oral capsules according to the conditions identified on the labels of each study drug, at room temperature (15°C to 25°C or 59°F to 77°F), with excursions permitted to (40°C or 104°F) in a secure area, free from environmental extremes, and with restricted access.

Sites will be instructed to store ATB200 lyophilized powder vials according to the conditions identified on the study drug label, at cold temperature (2°C to 8°C or 36°F to 46°F), with short excursions permitted to (25°C or 77°F) in a secure area, free from environmental extremes, and with restricted access.

Temperature logs must be maintained for the duration of the study. The temperature of the refrigerator where the ATB200 and alglucosidase alfa products are stored and the temperature of the storage room (or cabinet) where the AT2221 and placebo are stored must be recorded for each working day of the week the pharmacy personnel (or designated study personnel) is available. Temperature is required to be recorded using a standard min-max thermometer that has calibration records available (details usually contained within the device leaflet) and is maintained according to institutions standard maintenance policy.

The study drugs are to be stored only at the site(s) listed on Form FDA 1572 or Statement of Foreign Investigator form for non-US sites. Study drug is to be dispensed only to subjects who have provided written informed consent, have met all entry criteria, and are randomized using the interactive response technology (IRT).

Alglucosidase alfa will be stored in the same manner as described for ATB200. Placebo will be stored in the same manner as described for AT2221.

Because the vial sizes and appearance of ATB200 and alglucosidase alfa differ, vials should be kept inside of cartons (which appear identical between both product types) if possible while

being stored to avoid the potential of partial unblinding and should only be removed by an unblinded pharmacist at the time of reconstitution in an area with restricted access for unblinded staff. If it is not possible to keep the vials in the carton due to space limitations at a particular site, vials must be stored in a secure location in which only the unblinded pharmacist has access. Cartons containing ATB200/alglucosidase alfa should only be handled by unblinded staff because they may have slight differences in weight. Details of the storage conditions can be found in the pharmacy manual.

11.4. Study Drug Preparation

Instructions for preparation for oral product and infusion and the volume and rate of infusions will be provided in the pharmacy manual.

Only unblinded qualified personnel will handle and/or prepare the study drugs to maintain the integrity of the double-blind design of the study.

11.5. Administration

11.5.1. ATB200/Alglucosidase Alfa

The dose of ATB200/alglucosidase alfa is 20 mg/kg body weight. Dose will be calculated based on actual body weight, even if a subject's previous dose was based on lean body weight. The value for body weight will be obtained at the previous protocol-specified visit for obtaining weight.

ATB200/alglucosidase alfa does not contain any preservatives. Vials are single-use only. Reconstituted vials should be retained at the site until the monitor checks accountability.

ATB200/alglucosidase alfa is to be administered every 2 weeks as an approximate 4-hour IV infusion. Changes in the duration of ATB200/alglucosidase alfa infusion due to safety or tolerability issues will be documented. The total volume of infusion is determined by the subject's body weight. Instructions for preparation for infusion and the volume and rate of infusions will be provided in the pharmacy manual. Reconstitution of ATB200/alglucosidase alfa should be performed by unblinded qualified study personnel (eg, pharmacist or pharmacy technician or nurse under physician supervision). Intravenous administration of ATB200/alglucosidase alfa should be performed by qualified study personnel. Subjects should be carefully monitored during and after the first 3 infusions (Section 12.2.3). Any delegation of this responsibility must follow Section 16.3.4. Rate and duration of infusion must be constant for each infusion. Changes in the rate and/or duration of infusion due to safety or tolerability issues will be documented.

The protocol-specified administration of alglucosidase alfa is consistent with the Lumizyme Prescribing Information (August 2014) and the Myozyme Summary of Product Characteristics (December 2018).

11.5.2. AT2221/Placebo

The dose of AT2221 is 260 mg (4 capsules at the 65-mg strength) for subjects weighing ≥ 50 kg and 195 mg (3 capsules at the 65-mg strength) for subjects weighing ≥ 40 kg to < 50 kg.

The dose of placebo is 3 or 4 placebo capsules of the same size as AT2221, that is, size 2.

AT2221/placebo is administered orally, approximately 1 hour before ATB200/alglucosidase alfa infusion according to their treatment arm. Subjects will take 3 or 4 capsules of AT2221/placebo, depending on their body weight. Subjects should fast for at least 2 hours before and 2 hours after administration of AT2221/placebo. Fasting is defined as nothing by mouth except for water; this includes prescription or over-the-counter medications, vitamins, or herbal supplements other than premedications for administration of ATB200. Subjects should arrive at the clinic at least 1 hour prior to the start of the ATB200/alglucosidase alfa infusion to receive AT2221/placebo.

11.6. Randomization and Blinding

11.6.1. Randomization

The randomization code used in this study was generated and will be maintained by an external resource not involved with the conduct of the study.

11.6.2. Blinding

The following methods are used to maintain the blind of the investigator and site personnel, sponsor, and/or subject:

- use of IRT to randomly assign subjects to study drug and to calculate dose of study drug
- an unblinded pharmacist to handle and prepare the study drug
- an unblinded monitor to perform study drug accountability at the site
- an unblinded medical monitor to review select laboratory results that could potentially unblind a subject's treatment assignment
- black or dark covering over ATB200 and alglucosidase alfa reconstituted solution to be used during infusion
- a matching placebo for AT2221 to be used with alglucosidase alfa

11.6.3. Unblinding of Treatment Assignment

The medical care of subjects includes medical decisions, such as whether to start or stop treatment or institute alternative treatment, if required. In emergency situations, the investigator may need to unblind a subject's treatment assignment immediately using IRT (see the IRT manual) or as quickly as possible if he/she finds it is in the best interest of the subject. If IRT is unavailable or inaccessible at the time of an emergency unblinding, investigators are to contact IRT Technical Support, as described in the pharmacy manual. A subject's treatment assignment should be unblinded only if knowledge of the study drug administered will affect the treatment options available to that subject. It is the responsibility of the investigator to promptly document and explain any premature unblinding of treatment assignment to the Sponsor.

11.7. Study Drug Accountability

In accordance with local regulatory requirements, the investigator, designated site personnel, or head of the medical institution (where applicable) must document the amount of study drug dispensed and/or administered to study subjects, and the amount received from and returned to

Amicus (or designee), where applicable. Product accountability records must be maintained throughout the course of the study.

11.8. Study Drug Handling and Disposal

Because vials of ATB200 and alglucosidase alfa are distinguishable, the unblinded pharmacist or appropriately assigned unblinded designee will inventory and acknowledge receipt of all shipments of the study drugs. The investigator must keep an accurate record/log of the quantities of study drug dispensed and administered to each subject. The unblinded monitor will periodically check the supplies of study drugs held at the site to verify accountability of all study drugs used and to verify the drug accountability logs are completed and maintained in the investigator study file. The monitor will return all original containers of study drugs, whether empty or containing used or unused study drugs, to Amicus or their designee for destruction. Sites may not destroy study drugs on site unless Amicus has provided prior written approval.

11.9. Prohibited Medications

Use of the following medications is prohibited during this study:

- miglitol (eg, Glyset[®])
- non-study miglustat (eg, Zavesca[®])
- Myozyme or Lumizyme after treatment with ATB200/AT2221 has begun
- acarbose (eg, Precose[®] or Glucobay[®])
- voglibose (eg, Volix[®], Vocarb[®], or Volibo[®])
- any investigational/experimental drug

Subjects who are taking β_2 -receptor agonists or non-selective β -blockers (eg, propranolol, nadalol, carvedilol) before Day 1 must maintain a stable dose for the duration of the study.

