15.3.1. Analysis Populations

Safety Population: The safety population is defined as all subjects who receive at least 1 dose of study drug (ATB200/AT2221 or alglucosidase alfa/placebo). This population will be used in the assessment and reporting of safety data, and subjects will be analyzed according to the actual treatment received.

Intent-to-Treat Population: The intent-to-treat (ITT) population consists of all randomized subjects (regardless of whether they took a dose of study drug). This population will be analyzed according to the planned treatment groups. The ITT population is the primary population for efficacy analyses.

Modified Intent-to-Treat Population: The modified intent-to-treat (mITT) population consists of all randomized subjects who took at least 1 dose of study drug and have both a 6MWD baseline (ie, average of 2 screening 6MWD values) and at least one post-baseline 6MWD. This population will be analyzed according to the planned treatment groups. The mITT population will be used for supportive/sensitivity analyses of the primary and key secondary efficacy endpoints, as well as for baseline and demographic summaries.

Per-Protocol Population: The per-protocol population is a subset of the ITT population that consists of subjects who have no major protocol or site deviations that impact the analyses of the primary endpoints or the integrity of the study, and took only the study drug to which they were randomized. This population will be analyzed according to the planned treatment groups. The per-protocol population may be used in supportive/sensitivity analyses of the primary and/or key secondary endpoints.

Pharmacokinetic population(s) will be described in a separate modeling and simulation plan.

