6.1.6. Per-protocol Population

The per-protocol population (PP) is a subset of the mITT population consisting of any mITT subjects who do not have pre-specified protocol deviations that are considered important, as they potentially may have altered the subject's response to study treatment or confounded the study assessments, thereby impacting the analyses of the primary endpoint (6MWD) and the FVC. This population will be analyzed according to the actual treatment received.

The PP population will be characterized separately for sensitivity analyses for the 6MWD and % predicted FVC. The per-protocol population 1 (PP1) will be used for the sensitivity analyses of the 6MWD, while per-protocol population 2 (PP2) will be used for sensitivity analyses of the % predicted FVC.

Pre-specified important protocol deviations leading to exclusion from the PP1 and PP2 populations include those in [Table 2](#). These populations will be determined and finalized before locking the database.

Table 2: Pre-specified Important Protocol Deviations Leading to Exclusion from Per-protocol Populations (PP1 and PP2)

Item	Important Protocol Deviation Description (Excluded from PP1: for 6MWD)	Important Protocol Deviation Description (Excluded from PP2: for FVC)
1.	Subject did not have sufficient treatment exposure (ie, subject did not have at least 80% compliance with study treatment)	Subject did not have sufficient treatment exposure (ie, subject did not have at least 80% compliance with study treatment)
2.	Subject did not have the primary endpoint (6MWD) assessment at the Week 52 visit (including catch-up assessment or delayed visit) due to COVID-19 pandemic or other reasons	Subject did not have FVC assessment at the Week 52 visit (including catch-up assessment or delayed visit) due to COVID-19 pandemic or other reasons
3.	Subject was discontinued from the study for missing at least 5 infusions	Subject was discontinued from the study for missing at least 5 infusions
4.	Subject withdrew consent and/or discontinued from the study	Subject withdrew consent and/or discontinued from the study
5.	Subject was unblinded (accidentally or otherwise) before database lock	Subject was unblinded (accidentally or otherwise) before database lock
6.	Subject was inconsistent in the use/non-use of assisted devices during 6MWT	

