6.4. Handling of Intercurrent Events

Intercurrent events are defined as events that occur after treatment initiation and either preclude observation of the primary endpoint or affect its interpretation (eg, discontinuation of treatment, terminal events such as death, etc), per ICH E9 R1.

The potential intercurrent events for this study are listed in Table 5 together with the proposed strategy and handling of such events for the mixed-effect model repeated measures (MMRM) analysis and the analysis of covariance (ANCOVA).

Table 5: Accounting for Intercurrent Events

Intercurrent Event	Treatment Strategy for Handling Event	Handling of Event
Intervention for AEs, SAEs and IARs ^a ; Incorrect treatment assigned; Prespecified important major protocol deviations that can potentially affect the assessment of 6MWD.	Treatment policy strategy (based on ITT principle): 
 If subject continues in the study and dosing is resumed 	
For the ITT-OBS population: Value of interest (eg, 6MWD result observed at a given visit) will be used, regardless of whether the intercurrent event occurred. Note: No imputation will be performed for missing values at Week 52 (and other post-baseline visits). This is for the MMRM analysis.
 
For the ITT-LOCF population: Value of interest will be used, regardless of whether the intercurrent event occurred. Note: Missing values at Week 52 (and other post-baseline visits) will be imputed with the last available post-baseline assessment value. This is for the ANCOVA analysis.
 
Example: Compare “Treat A + Use of prohibited concomitant medication as needed” versus “Treat B + Use of prohibited concomitant medication as needed.”

	
 If subject permanently discontinues from study drug (and is withdrawn from the study) 	
For the ITT-OBS population: Observed value at time of discontinuation will be used. Note: No imputation will be performed for missing values at Week 52 and other post-baseline visits. Data after study discontinuation will be considered missing and will be handled by the MAR assumption in the MMRM analysis.
 
For the ITT-LOCF population: The last available assessment value will be used (regardless of whether the intercurrent event occurred). This setup is for the ANCOVA analysis.

Table 5: Accounting for Intercurrent Events (Continued)

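### The ban on commercial alglucosidase alfa in protocol 11.9 is worded by blinded arm, and the SAP drops the per-protocol condition that would exclude subjects who took it

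*Protocol*

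**What the plan says.** **The prohibition.** Protocol 11.9 lists as prohibited "Myozyme or Lumizyme after treatment with ATB200/AT2221 has begun". Another entry in the same list begins "non-study miglustat (eg, Zavesca", which is worded by source of supply and does not depend on arm.

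**The control product.** Protocol 11.1 states: "Alglucosidase alfa (Myozyme/Lumizyme) functions as ERT". The brands in 11.9 are therefore also the control arm's study drug.

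**The blind.** Protocol 11.6.2 opens: "The following methods are used to maintain the blind of the investigator and site personnel, sponsor, and/or subject".

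**The intended switch.** The synopsis and 8.1 have ERT-experienced subjects stay on their alglucosidase alfa through screening and then move to the assigned study drug. Both arms are named.

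**The per-protocol set.** Protocol 15.3.1 requires that subjects "took only the study drug to which they were randomized" and analyses them by planned group. SAP 6.1.6 instead excludes subjects with deviations listed in Table 2, and adds: "This population will be analyzed according to the actual treatment received". SAP section 2 says that the SAP's analyses take precedence over the protocol's.

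**The concern.** Two separate things look wrong.

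First, a rule in a double-blind protocol should be one that blinded staff can apply from what they can see. This one is triggered by the start of one particular arm. No other listed rule plainly fills the gap. Exclusion criterion 1 exempts alglucosidase alfa, and the 11.9 entry on investigational drugs does not clearly reach a marketed product.

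Second, the SAP says that the per-protocol sets exist to remove deviations that could have changed response or confounded assessment. Commercial alglucosidase alfa taken during the treatment period is such a deviation. In the experimental arm it is exposure to the comparator; in the control arm it is unassigned extra or substitute product. The protocol's definition would have removed these subjects. The SAP's does not.

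The setting makes this more than theoretical. Outside the Australian variant, ERT-experienced subjects have had at least 24 months of alglucosidase alfa before entry, and both documents expect runs of missed study infusions during the pandemic.

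**Working it through.** **Step 1: whom 11.9 covers, read literally**

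| | Experimental arm | Control arm |
|---|---|---|
| Has ATB200/AT2221 begun? | Yes, from Day 1 | Never |
| Is the 11.9 entry triggered? | Yes | No |
| Does 8.1 have prior ERT give way to study drug? | Yes, if ERT-experienced | Yes, if ERT-experienced |

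The second and third rows disagree for the control arm. Section 8.1 describes a switch; it does not state a prohibition, and it is silent on ERT-naïve subjects.

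**Step 2: per-protocol definitions**

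| | Protocol 15.3.1 | SAP 6.1.6 and Table 2 |
|---|---|---|
| Randomized study drug only | Required | Not stated |
| Prohibited medication | Covered where it is non-study ERT, or where it is a major deviation affecting the primary endpoint | No item |
| Analysed by | Planned group | Actual treatment |

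**Step 3: would the existing Table 2 items catch such a subject anyway?**

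The plan's thresholds are compliance below 80% and discontinuation for at least 5 missed infusions. SAP 9.4.2 gives planned infusions as (last on-treatment date − first infusion date + 14)/14.

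- Day 1 to Day 365: (364 + 14)/14 = 378/14 = 27 planned.
- Four missed: 23/27 = 85.2%, which passes.
- If the last on-treatment date is Week 50 (Day 351): (350 + 14)/14 = 26 planned, and 22/26 = 84.6%, which passes.
- If all four misses are COVID-related, SAP 9.4.2 subtracts them. Taken from the planned count, that gives 23/(27 − 4) = 100%.
- Commercial product taken on top of full study dosing: 27/27 = 100%.

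Dose-based compliance gives the same percentages if each infusion carries the same dose.

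Four consecutive misses leave 5 × 2 = 10 weeks between study doses. That is 8 weeks beyond the usual interval, or 8/52 = 15% of the treatment period.

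Take a subject who misses four, receives commercial product in the gap and then completes Week 52:

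- Item 1 (compliance): 85%, not excluded.
- Item 2 (no Week 52 assessment): assessed, not excluded.
- Item 3 (discontinued for at least 5 missed): four missed, not excluded.
- Item 4 (withdrew or discontinued): no.
- Item 5 (unblinded): not implied.
- Item 6 (assistive device, PP1 only): unrelated.

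The subject stays in PP1 and PP2.

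**Step 4: what does not move**

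The sample-size statement reproduces: 66 versus 33 at a standardized effect of 0.7 and two-sided 0.05 gives 90.2% power by the exact t calculation, and 99/0.9 = 110. Nothing here alters it. With no rate of non-study ERT use in either document, no bias or power loss can be calculated.

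**The case against.** The strongest reply is that the protocol as a whole is clear enough. A blinded site can comply by applying the ban to every subject once dosing starts. Some time trigger is needed because ERT-experienced subjects take alglucosidase alfa during screening, and a flat ban by brand name would prohibit the control drug itself. The protocol also uses ATB200 elsewhere as shorthand for the blinded infusion, for example in the home-infusion and PK-sampling sections. All of this stands, and it is why the clause is a wording defect.

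A reader might infer more than the documents support:

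- *That control subjects may take commercial product with no deviation.* Section 13.3.3 records a missed study infusion as a deviation in either arm. Table 8 fixes the control regimen, and 13.3.2 makes dosing 20% or more above the assigned dose reportable.
- *That such use would go unseen.* Concomitant medications are recorded at treatment visits (Table 10, 12.3.3), and SAP 7.3 has deviations reviewed throughout.
- *That a given share of control data is contaminated.* No count exists, and any percentage would be conjecture.
- *That 11.5.2 has the same fault.* Its fasting exemption, "other than premedications for administration of ATB200", reads as the same shorthand, and no consequence is shown.
- *That Table 5 overlooks the event.* Its event column already includes prespecified important deviations, and "Use of prohibited concomitant medication as needed" is its worked example under treatment policy.

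It is also fair to say that Table 2's lead-in does not claim to be exhaustive and that the sets are finalized before database lock. An item could still be added. As written, though, nothing removes these subjects.

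**Conclusion.** The point holds in two limited parts. Protocol 11.9 is literally arm-dependent in a blinded trial and does not match 8.1. The SAP drops a per-protocol condition that the protocol contained, and the remaining Table 2 items need not replace it.

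The reach is small. The per-protocol ANCOVA is one of six sensitivity rows in SAP Table 7 for each of 6MWD and % predicted FVC. The primary MMRM uses observed data regardless of intercurrent events, so its method and population are unaffected. No reader should conclude that the primary result is at risk.

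The change from planned to actual treatment matters mainly in the experimental arm. A subject there who also took commercial alglucosidase alfa has received both products, and SAP 6.1.6 gives no rule for assigning that subject. In the control arm the product is the same, so the ambiguity does not arise.

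The 85% figure assumes a full 52-week course with four missed infusions. The number of subjects affected is unknown and could be zero.

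**What to change.** 1. **Protocol.** Reconcile 11.9 with 8.1, 11.1 and 11.6.2 so that the clause does not depend on a blinded assignment. What the rule should be is the sponsor's clinical decision and is not proposed here.
2. **SAP Table 2.** Restore the 15.3.1 condition by adding one important deviation for both PP1 and PP2: receipt, from Day 1 on, of non-study ERT or another medication prohibited by 11.9 as reconciled. Counting from Day 1 keeps screening-period alglucosidase alfa in ERT-experienced subjects from triggering it. The addition also brings the Table 5 row into line with its own example.
3. **Planned or actual.** Make protocol 15.3.1 and SAP 6.1.6 agree on how per-protocol subjects are grouped. If actual treatment is kept, say how a subject who received both products is classified.

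The cost is wording in one protocol clause, one line in Table 2 and one sentence in SAP 6.1.6. The medication data are already collected. The downside is that PP1 and PP2 may lose a few subjects. The changes should be settled before database lock, when the SAP says these sets are finalized.
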